2.14.3 EDSS

The change from baseline in EDSS will be summarized descriptively by visit window, as well as by visit window and last prior DMT.

2.14.4 Number of T1 Gd-enhancing lesions per scan

Number of Gd-enhancing lesions will be obtained from each MRI scan per protocol assessment schedule. To estimate the number of Gd-enhancing lesions per scan, below variables will be derived.

- The total number of Gd-enhancing lesions will be derived by taking the sum of numbers of Gd-enhancing lesions from all scheduled MRI scans. MRI scans taken within 14 days after the termination of steroid therapy will not be included in analysis of Gd lesion related endpoint.
- The number of MRI scans will be derived by counting the number of scheduled MRI scans with non-missing values for the number of Gd-enhancing lesions.

The mean number of T1 Gd-enhancing lesions per scan and corresponding 95% CI will be estimated using a negative binomial model with log-link with number of relapses in previous year, baseline EDSS, baseline number of T1 Gd-enhancing lesions, the participant's age at baseline and prior MS therapies (fumarates and Fingolimod) as covariates. In addition, separate estimates of T1 lesions and corresponding 95% CIs for last prior DMT (fumarates and fingolimod) and for last prior DMT and duration of washout will be given. In case model has convergence issues, covariates will be dropped with the following order: 1) Number of relapses in previous year; 2) Baseline EDSS; 3) Age. Time-based and subject-based T1 Gd-enhancing lesions will also be summarized.

The reduction rate of mean number of T1 Gd-enhancing lesions per scan over time vs baseline will be estimated using a Generalized Estimating Equation (GEE) for a negative binomial model with log-link and natural log the number of MRI-scans with evaluable Gd-enhancing lesions at each visit as an offset variable, and with number of relapses in previous year, baseline EDSS, the patient's age at baseline and prior MS therapies as covariates. In this analysis, outcome will also include number of T1 Gd-enhancing lesions at baseline, the reduction rate vs baseline will be derived using contrast. The negative binomial model will also be performed by prior MS therapy subgroups. In this analysis, separate models will be implemented for each subgroupDetails of negative binomial GEE models and SAS codes are given in Section 5.4.3.

2.14.5 Number of new or enlarging T2 lesions on MRI per year (annualized T2 lesion rate)

The number of new or enlarging T2 lesions as compared to the previous MRI scan will be obtained from each MRI scan per protocol assessment schedule. To estimate the annualized rate of new or enlarging T2 lesions, below variables will be derived:

- The total number of new or enlarging T2 lesions will be derived by taking the number of new or enlarging T2 lesions from the last scheduled MRI scan with a non-missing value.
- The time (in years) from previous MRI scan will be calculated as (date of last scheduled MRI scan with a non-missing value for the number of new or enlarging T2 lesions—date of previous MRI scan +1) / 365.25.

The mean number of new or enlarging T2 lesions on MRI per year and corresponding 95% CI will be estimated using a negative binomial model with log-link and time from previous MRI scan (as natural log of time in years) will be used as an offset with number of relapses in previous year, baseline EDSS, baseline T2 lesion volume, the participant's age at baseline and prior MS therapies (fumarates and Fingolimod) as covariates. In addition, separate estimates of T2 lesions and corresponding 95% CIs for last prior DMT (fumarates and fingolimod) and for last prior DMT and duration of washout will be given. In case model has convergence issues, covariates will be dropped with the following order: 1) Number of relapses in previous year; 2) Baseline EDSS; 3) Age. Time-based and subject-based new or enlarging T2 lesions will also be summarized.

The reduction rate of mean annulized rate of new or enlarging T2 lesions over time vs baseline will be estimated using a Generalized Estimating Equation (GEE) for a negative binomial model with log-link and natural log of the time from previous MRI scan as an offset variable, and with baseline T2 lesion volume, baseline EDSS, the patient's age at baseline and prior MS therapies

as covariates. The negative binomial model will also be performed by prior MS therapy subgroups. In this analysis, separate models will be implemented for each subgroup. Details of negative binomial GEE models and SAS codes are given in Section 5.4.3.

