8.1 Screening

The Screening period, including baseline visit, can last up to 60 days and consists of assessments used to determine subject eligibility and including the transition period from any fumarate-based RMS approved therapy or fingolimod (Section 6.6.1). In order to allow adequate time to obtain results and confirm subject eligibility, the Baseline and Day 1 visits should not be conducted on the same day.

Subjects may be rescreened if they do not initially meet eligibility criteria. All assessments must be repeated, except for MRI (the original MRI may be used during rescreening if the rescreening occurs within 3 months of the original MRI date). If a subject is re-screened, a new ICF must be obtained and re-screening will be documented in the subject's source documents. A new subject number will be allocated and the site will record the data in a new CRF.

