8.3.4 Magnetic Resonance Imaging (MRI)

All subjects will undergo MRI scanning of the brain according to the schedules in Table 8-1.

MRI scans will be read by the central MRI reading center. Prior to the start of the study, MRI technician from each center will receive an MRI Manual, outlining technical implementation, image quality requirements and MRI administrative procedures.

The site will be asked to program the MRI scanner that is designated for evaluation of the study subjects. Site will be asked to perform and submit a dummy scan (so called "dummy or dry run") to the central MRI reading center to assess the image quality and to evaluate the compatibility of the electronic data carrier. Once the dummy run has been accepted, all the parameter settings for the study specific MRI sequences must remain unchanged for the duration of the study. Finally, if the site is already pre-approved for performing conventional MRI scan sequences by the imaging vendor the dummy or dry run may be skipped.

Each MRI scan performed for the study needs to be previewed by a local neuro radiologist. During the study, the quality of each scan performed will be assessed by the central MRI reading center. The MRI scan should be sent to the central MRI reading center upon completion of each individual scan. As soon as the scan is received by the central MRI reading center, it will be evaluated for quality, completeness and adherence to the protocol. Confirmation of MRI quality or a description of the quality problems, if detected, will be communicated to the site. If a scan is incomplete or incorrectly performed, the study center will be asked to repeat it as soon as possible. After completion of the quality check, all scans will be analyzed according to the MRI protocol.

Restrictions to MRI schedule

To avoid interferences caused by steroids (in regards to Gd+ enhancing lesions) for the treatment of MS relapse, the following restrictions apply for this study:

- In case of relapse, if an MRI has been scheduled within 14 days of the initiation of steroid treatment, MRI (with Gd+ enhancement) should be performed before steroid treatment is initiated.
- No MRI (with Gd+ enhancement) should be performed while a subject is on steroid therapy for relapse and within the following 14 days upon termination of steroid treatment.

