2.1.1 General definitions

Below some general definitions to be used in the rest of the document are summarized.

Table 2-1 General Definitions

Table 2-1 General Deminitions	
Study treatment/Study drug	The investigational drug (ofatumumab) will be referred as study treatment or study drug.
Date of first administration of study drug/first dose date	The first dose date of active study drug administration.
Date of last administration of study drug/last dose date	The last dose date of active study drug administration.
Study Day 1 or Day 1	The date of first administration of study drug/first dose date.
Study Day	 All other study days will be labeled relative to Day 1. For events with dates on or after Day 1, study day for the event is calculated as (event start date – first dose date + 1). For events with dates before Day 1, study day for the event is calculated as (event start date – first dose date). Day 0 will not be used.
Duration of an event	Duration of an event is calculated as (event end date – event start date +1).
1 month	30 days; to be used in defining 6-month confirmed disability worsening or improvement.
4 weeks	28 days; to be used in determining target days of scheduled visits. It is based on the scheduled injection frequency for ofatumumab (during the maintenance phase).
Day post-study drug discontinuation	Day post-study drug discontinuation for a particular event is calculated as (event start date – study drug discontinuation date).
Baseline	Baseline is the last assessment obtained prior to the first administration of study drug. No visit windows will be needed for the identification of baseline assessment.
	For pulse and blood pressure vital sign values, the baseline is the average of the non-missing values of the 3 measurements taken on the last visit prior to the first administration of study drug. The pre-injection assessment values on Day 1 vital sign case report form (CRF) page will not be used for baseline derivations.

On-treatment period	On-treatment period includes days from the first injection date until 30 days after the last injection date. This definition considers subjects on ofatumumab are scheduled to inject every 28 +/- 3 days. For calculation of compliance to study drug administration, similar definition of on-treatment period will be used.

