2.3.3 MS baseline disease characteristics

MS baseline characteristics, MS disease history and MS medication history will be summarized for the FAS. MS baseline characteristics include baseline EDSS, 9HPT, T25FW, CCL LCVA, key MRI parameters (e.g., number of Gd-enhancing T1 lesions, number of T2 lesions, T2 lesion volume), Biomarkers such as NfL and IgG, IgM, CD-19 B-cell counts, Lymphocytes and neutrophils.

Baseline lymphocyte and neutrophil values should also be summarized, including reporting of lymphocyte and neutrophil abnormalities (Table 2-12).

Of note, laboratory values below limit of quantification (e.g. value coded as <x.xx) will be imputed to the lower limit of quantification/2. MS baseline disease characteristics will also be summarized by last prior DMT.

Table 2-12 Notable abnormalities for lymphocyte and neutrophil counts

Lymphocytes (10E9 /mL)	Decrease in lymphocytes counts: Gr1: <lln -="" 0.2="" 0.5="" 0.8="" 10e9="" <0.5="" <0.8="" gr2:="" gr3:="" l="" l<="" th="" x=""></lln>
	Gr4: <0.2 x 10E9/L Increase in lymphocytes counts: >4.0 - 20 x 10E9 /L (grade 2 lymphocytosis) >20 x 10E9 /L (grade 3 lymphocytosis)
Neutrophils (10E9 /mL)	Decrease in neutrophils counts: Gr1: <lln -="" 0.5="" 1.0="" 1.5="" 10e9="" <0.5="" <1.0="" <1.5-="" gr2:="" gr3:="" gr4:="" l="" l<="" td="" x=""></lln>

MS disease history includes duration of MS since diagnosis (years), duration of MS since first symptom (years), number of relapses in the last 12 months prior to screening, number of relapses in the 12 to 24 months prior to screening, type of MS at study entry (i.e., RRMS or SPMS), time since onset of SPMS, time since onset of most recent relapse (months), and number of prior DMTs.

Duration of MS since diagnosis (years) will be derived [(first dose date – MS diagnosis start date + 1)/365.25]; duration of MS since first symptom (years) will be derived as [(first dose date – first MS symptom date +1)/365.25]; time since onset of SPMS (years) will be derived as [(first dose date – conversion to SPMS date +1)/365.25]; and time since onset of most recent relapse (months) will be derived as [(first dose date – most recent relapse onset date + 1)/(365.25/12)]. In these calculations, partial dates if any will be imputed according to the rules specified in Section 5.1.4.1.

MS medication history of previous disease-modifying drugs (coded by WHO drug dictionary) will be summarized by preferred term (PT).

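### SAP 2.14.5 plans a reduction in the new/enlarging T2 lesion rate versus baseline, but the schedule has no pre-treatment scan interval from which a baseline rate could come

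*SAP*

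**What the plan says.** SAP 2.14.5 defines the outcome by scan pairs: "The number of new or enlarging T2 lesions as compared to the previous MRI scan will be obtained from each MRI scan". The repeated-measures analysis in that section is a negative binomial GEE with the "natural log of the time from previous MRI scan as an offset variable". Its stated aim is: "The reduction rate of mean annulized rate of new or enlarging T2 lesions over time vs baseline will be estimated". The model is repeated within prior-therapy subgroups, and the section refers to SAP 5.4.3 for model details and code.

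SAP 2.1.1 fixes the meaning of the reference: "Baseline is the last assessment obtained prior to the first administration of study drug". For MRI this is the screening scan. Protocol 8.3.4 says "All subjects will undergo MRI scanning of the brain according to the schedules in Table 8-1", and that table marks MRI at Screening, Week 24, Week 48 and the end-of-study visit (Week 96). Its Baseline and Visit 1 columns are empty in the MRI row.

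SAP 2.14.4, the matching analysis for Gd-enhancing T1 lesions, contains a sentence that 2.14.5 lacks: "outcome will also include number of T1 Gd-enhancing lesions at baseline". It then derives the reduction by a contrast. Among the baseline MRI parameters, SAP 2.3.3 names as examples "number of Gd-enhancing T1 lesions, number of T2 lesions, T2 lesion volume".

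**The concern.** A lesion is new or enlarging only by comparison with an earlier scan. A rate at baseline would need two scans before the first dose, and the schedule has one. The Gd-enhancing analysis does not have this difficulty, because enhancing lesions are counted on a single scan and the screening scan supplies a value. Section 2.14.5 states the same kind of comparison for an outcome that has no value at screening.

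The trial has no control arm, so a published T2 reduction from baseline would naturally be read as the effect of switching to ofatumumab. If the reference is left open, someone has to choose it when the model is programmed. Any stand-in would carry a label that the data do not support, and it would carry over into the separate fumarate and fingolimod models.

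**Working it through.** The plan gives no figure for this analysis, so there is none to reproduce. The check is whether the contrast can be estimated, and then what the nearest available reference contains.

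**Inputs.** Outcome and offset: SAP 2.14.5. Baseline: SAP 2.1.1. Scan times: Protocol Table 8-1 (Screening on Day -60 to -8; Week 24 on Day 168 ± 14; then Weeks 48 and 96). SAP Table 2-4 has matching MRI windows for Weeks 24, 48 and 96.

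**Step 1: which scans yield an observation.**

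| Scan | Earlier scheduled scan | T2 count and offset | Gd-enhancing count |
|---|---|---|---|
| Screening (baseline) | none | neither defined | yes |
| Week 24 | Screening | yes | yes |
| Week 48 | Week 24 | yes | yes |
| Week 96 | Week 48 | yes | yes |

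**Step 2: estimability.** Code visit with four levels in cell-means form, ordered baseline, Week 24, Week 48, Week 96. A contrast is estimable only if it lies in the row space of the design matrix.

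- T2: the rows are (0,1,0,0), (0,0,1,0) and (0,0,0,1), so the rank is 3 for four levels. Week 24 minus baseline is (-1,1,0,0). Its first entry is not zero, while every row has zero there, so it is not estimable. The same holds for Week 48 and Week 96 minus baseline.
- T2: Week 48 minus Week 24, (0,-1,1,0), and Week 96 minus Week 24, (0,-1,0,1), are estimable.
- Gd-enhancing: all four rows are present, the rank is 4, and all baseline contrasts are estimable.

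**Step 3: what the Screening-to-Week-24 interval contains.** There is no Day 0. A scan on Day -s is s days before Day 1, and Day 168 is 167 days after it. SAP 2.14.5 adds one day when it computes time between scans, so the interval is s + 167 + 1 = s + 168 days.

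- Scan on Day -8: 8/176 = 4.5% before first dose.
- Scan on Day -60: 60/228 = 26.3% before first dose.
- Using the 14-day visit window: Day -8 to Day 182 gives 8/190 = 4.2%; Day -60 to Day 154 gives 60/214 = 28.0%.

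The share can be larger for a rescreened subject, since Protocol 8.1 says "the original MRI may be used during rescreening if the rescreening occurs within 3 months of the original MRI date".

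**Step 4: what a ratio against that interval estimates.** Let p be the pre-dose share, a the lesion rate before the first dose and b the rate after it, taken as constant. The first-interval rate is then p·a + (1 - p)·b, and the ratio of a later interval to it is b / [p·a + (1 - p)·b]. This equals b/a only if p = 1 or a = b. With p between about 0.05 and 0.26 it is a comparison of later with early follow-up, not of after with before. The pre-dose days are also not necessarily time on the previous drug, because the screening period includes the transition off it (Protocol 6.6.1).

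**The case against.** The strongest reply is that the public copy is incomplete. SAP 2.14.5 sends the reader to 5.4.3, which appears only as a heading, and the list under SAP section 4 is also not visible. The full SAP may name a reference interval there. That is a fair limit, and nothing here treats the missing text as an omission. But a reference placed on the first on-study interval would not be baseline as SAP 2.1.1 defines it, so the wording of 2.14.5 would still need to change.

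Second, historical scans may exist. New or enlarging T2 lesions are one way to meet inclusion criterion 8, and a subject rescreened after more than three months would have a second pre-treatment scan. The SAP also says previous MRI scan, not previous study scan, and the MRI manual is not available. So it cannot be said that no earlier scan exists for anyone. Neither visible document, however, describes such scans as an analysis input or provides for their central reading. They would be available only for some subjects, and where they were the basis for eligibility they were selected for activity, which invites regression to the mean.

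Third, the list in SAP 2.3.3 is only of examples, so the absence of a new/enlarging count there is weak evidence. The finding does not need it.

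A reader might infer that the total T2 lesion count at screening would be used as the baseline value and would produce a spurious near-complete reduction. The documents do not support that: nothing proposes it, and a single screening scan has no offset in this model. Likewise, the upper end of the pre-dose share is an extreme. Table 8-1 (footnote 10) places the MRI after the other screening eligibility assessments, so few scans should fall on Day -60, and a re-used scan followed by a full screening period would be rarer still.

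**Conclusion.** The point stands. From scheduled data, the T2 reduction against baseline as the SAP defines it is not estimable: there are no pre-treatment intervals and three later ones. Comparisons of Week 48 and Week 96 with the Screening-to-Week-24 interval are estimable, but that interval is mostly on treatment, with about 5% to 26% of it before the first dose. The conclusion rests on the visible schedule and definitions, and on no historical scan being collected under documents that cannot be seen.

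Its reach is limited. A reader might infer that the MRI analyses or NEDA-3 as a whole are unsound; they are not, on this point. The endpoint is exploratory, and Protocol 12.6 plans only descriptive summaries of T2 lesions. The primary relapse-rate test, the overall annualised T2 rate and the Gd-enhancing reduction do not depend on this contrast. Nor do the documents announce a before/after-switch claim for T2 lesions. The risk is that the present wording would invite one. The change should be made, but the trial's main conclusion does not turn on it.

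**What to change.** In SAP 2.14.5, replace *over time vs baseline* with annualised rates by interval from the same GEE: Screening to Week 24, Week 24 to 48, and Week 48 to 96.

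- Define the rate ratios as each later interval against Screening-to-Week-24, and label them so in tables and text, including the prior-therapy subgroup models.
- State that the first interval includes time before the first dose, and summarise how much.
- Report the Week 24 to 96 rate as the clean on-treatment rate.
- Make no before/after-switch claim for new or enlarging T2 lesions.
- Bring the code in 5.4.3 into line if it names a different reference.

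The cost is SAP wording and one change of contrast. The scans, counts and model are already planned, and no new data are needed. What is lost is a T2 reduction-from-baseline estimate, which the scheduled scans cannot supply.

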2.14.6 Change from baseline in T2 lesion volume

Raw T2 lesion volume and change from baseline in T2 lesion volume will be summarized by visit window. The mixed model for repeated measures (MMRM) model will be fitted, using log-transformed change from baseline T2 lesion volume as the outcome, adjusting for last prior DMT and visit as factors, log-transformed baseline T2 lesion volume, baseline EDSS and subject's age at baseline as continue covariates. Unstructured correlation matrix will be specified within the model. Estimates for each visit window, as well as 95% CI and p-values will be given. This analysis will also be repeated by last prior DMT. In case model has convergence issues, the following actions will be taken: 1) Drop age; 2) Change the covariance structure from unstructured to Autoregreesive(1). Details of MMRM model and SAS codes will be provided in Section 5.4.4.

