2.14.10 Biomarkers (NfL)

Serum Neurofilament (NfL) concentration will be explored related to biomarker for MS. Change in NfL concentration will be summarized by visit descriptively using FAS. The arithmetic mean, arithmetic standard deviation, the mean, median, min, max, Geometric-mean, the coefficient of variation of arithmetic mean (%) and the coefficient of variation of the Geometric-mean (%), will be reported in descriptive summaries. In addition, NfL will also be summarized by visit and last prior DMT (fumarates vs. fingolimod). The mixed model for repeated measures (MMRM) on log-transformed change from baseline NfL will also be fitted, with last prior DMT and time points as factors, baseline age and the log-transformed NfL baseline concentration as continuous covariates. Unstructured correlation matrix will be specified within the model. Estimates for each time point, as well as 95% CI and p-values will be given. This analysis will also be repeated by last prior DMT. In case model has convergence issues, the following actions will be taken: 1) Drop age; 2) Change the covariance structure from unstructured to Autoregreesive(1). Details of MMRM model and SAS codes will be given in Section 5.4.4.

Serum CCI will be analyzed separately outside of CSR.

[figure not shown]

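### Do SAP 2.14.6 and 2.14.10 ask for the log of a difference when they name the MMRM outcome for T2 lesion volume and NfL?

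*SAP*

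**What the plan says.** SAP 2.14.6 starts with descriptive output: "Raw T2 lesion volume and change from baseline in T2 lesion volume will be summarized by visit window". It then fits an MMRM "using log-transformed change from baseline T2 lesion volume as the outcome". Last prior DMT and visit are factors, and the continuous covariates are "log-transformed baseline T2 lesion volume", baseline EDSS and age. On output it says: "Estimates for each visit window, as well as 95% CI and p-values will be given".

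SAP 2.14.10 does the same for serum NfL: "The mixed model for repeated measures (MMRM) on log-transformed change from baseline NfL will also be fitted", with "baseline age and the log-transformed NfL baseline concentration as continuous covariates". Its descriptive summaries include the geometric mean and "the coefficient of variation of the Geometric-mean". It promises the same output: "Estimates for each time point, as well as 95% CI and p-values will be given".

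Neither section writes the outcome as a formula. Both refer the reader to SAP 5.4.4 for the model details and SAS code. In the public copy only the heading of 5.4.4 can be read. The SAP's document history for Amendment 4 lists changes to the T2 lesion volume and NfL analysis methods and to the sample code in 5.4.4.

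**The concern.** The order of the words invites a literal reading. In 2.14.6 the sentence just before the model uses change from baseline beside the raw volume, where it most naturally means the plain difference. Putting a log in front of that gives log(post minus baseline).

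That quantity is a poor outcome for three reasons:

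- It is undefined whenever a patient is stable or improves, so the model would keep only visits at which the value rose.
- It depends on the unit of measurement.
- Zero on its scale does not mean no change. If the p-values test a visit mean of zero (the visible text does not state the null), they would test a rise of exactly one unit.

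The trial has a single arm, so no control contrast exists in which a unit constant could cancel. If the literal formula were run, the visit estimates, confidence intervals and p-values for both markers would be uninterpretable.

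**Working it through.** The documents give no sample size, power or alpha for these models, so there is no figure of the plan's own to reproduce. The check compares the two readings and then asks which one the text supports.

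**Inputs.** The outcome and covariate wording comes from SAP 2.14.6 and 2.14.10. The volumes below are illustrative and are not taken from the documents.

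**Formulas.** Let B be the baseline value and P the post-baseline value.

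- Literal reading: L = ln(P - B)
- Log-scale reading: R = ln(P) - ln(B) = ln(P/B)

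| B to P | L, in cm3 | L, in mm3 | R, either unit |
|---|---|---|---|
| 5.0 to 5.5 cm3 | ln(0.5) = -0.693 | ln(500) = 6.215 | ln(1.1) = 0.095 |
| 5.0 to 4.5 cm3 | undefined (P - B = -0.5) | undefined | ln(0.9) = -0.105 |

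Moving from cm3 to mm3 adds ln(1000) = 6.908 to every L that exists and adds 0 to R. An outcome of zero means P - B = exp(0) = 1 unit under L, and P/B = 1 under R.

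**Share of visit values with no L.** Assume that P/B is log-normal with median m and SD s on the log scale; this assumption has no source in the documents. The share with P at or below B is then Phi(-ln(m)/s).

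| m | s = 0.1 | s = 0.2 | s = 0.3 | s = 0.4 |
|---|---|---|---|---|
| 0.95 | 0.696 | 0.601 | 0.568 | 0.551 |
| 1.00 | 0.500 | 0.500 | 0.500 | 0.500 |
| 1.05 | 0.313 | 0.404 | 0.435 | 0.451 |

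The literal reading would therefore be unworkable. The next step is whether the plan asks for it.

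**Which reading the text supports.**

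1. Both models carry ln(B) as a covariate. This fits R exactly. If R = a + b ln(B), then ln(P) = a + (b + 1) ln(B), so the model is the usual baseline-adjusted analysis on the log scale. L has no such relation to ln(B).
2. SAP 2.14.10 reports geometric means and their coefficient of variation for NfL. These are summaries for data analysed on the log scale.
3. SAP 2.14.6 says raw for the descriptive part and log-transformed for the model. Log-transformed can fairly be read as naming the scale on which change is taken.
4. The details are assigned to SAP 5.4.4. That content exists in the plan but is not readable in the public copy, so its absence is not a gap in the plan.

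**Would a wrong reading go unnoticed?** It is unlikely. Under L every unchanged or falling value returns a missing outcome. With a median ratio near 1 that is about half the records, and an analyst would see it on the first run.

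**The case for a change.** The strongest case for a change is that a SAP should define its outcomes without help from context. The same phrase means the raw difference one sentence earlier, and the SAP is explicit about logs elsewhere, for example where it sets the offset of the relapse-rate model. Protocol 12.6 promises adjusted repeated-measures estimates for T2 lesion volume, so the T2 model delivers something the protocol specifies. The text does not say whether estimates will be back-transformed, or what null the p-values test. Stating the formula would cost one sentence per section.

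Some of this stands: the wording is loose, and the literal formula could not be used. It does not show that anything would be analysed wrongly. If the code uses the log ratio, rewording alters no output, and nothing visible suggests that the code does otherwise. The loss percentages, the unit shift and the one-unit null all describe a calculation that the covariates argue against. Back-transformation to ratios is a reasonable way to report, but the documents do not show that it is missing from 5.4.4. A rule for zero lesion volume, where the log-baseline covariate would also fail, is a separate point that matters only if a zero occurs, and no section suggests that one would.

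**Conclusion.** The concern does not call for a change. The phrase in SAP 2.14.6 and 2.14.10 is common shorthand for change from baseline on the log scale. The log-transformed baseline covariates in both models, and the geometric means for NfL, make that the natural reading, and a competent analyst would program it that way.

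If that reading is the one programmed, the effect on results is nil. Both models are exploratory, carry no stated alpha or decision rule, and sit beside descriptive summaries by visit. The primary analysis of annualized relapse rate uses neither model.

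This conclusion rests on two things: that SAP 5.4.4, which cannot be read in the public copy, follows the log-scale meaning, and that the literal version would be noticed because it fails on every non-increase. The first cannot be confirmed from the documents, but nothing in them contradicts it.
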